### For Patients with Non-Measurable Disease (i.e., Non-Target Disease)

| Non-Target Lesions  | New Lesions | Overall Response |
|---|-------------|------------------|
| CR  | No          | CR               |
| Non-CR/non-PD   | No          | Non-CR/non-PD*   |
| Not all evaluated   | No          | not evaluated    |
| Unequivocal PD  | Yes or No   | PD               |
| Any   | Yes         | PD               |
| 
* ‘Non-CR/non-PD’ is preferred over ‘stable disease’ for non-target disease since SD is increasingly used as an endpoint for assessment of efficacy in some trials so to assign this category when no lesions can be measured is not advised
 |             |                  |

#### 10.1.5 Duration of Response

**Duration of overall response:** The duration of overall response is measured from the time measurement criteria are met for CR or PR (whichever is first recorded) until the first date that recurrent or progressive disease is objectively documented (taking as reference for progressive disease the smallest measurements recorded since the treatment started).

The duration of overall CR is measured from the time measurement criteria are first met for CR until the first date that progressive disease is objectively documented.

Duration of stable disease: Stable disease is measured from the start of the treatment until the criteria for progression are met, taking as reference the smallest measurements recorded since the treatment started, including the baseline measurements.

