#### **10.1.6 Progression-Free Survival**

Progression-Free Survival (PFS) is defined as the duration of time from start of treatment to time of progression or death, whichever occurs first.

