## 12.4 Analysis of Secondary Endpoints

There are 5 Secondary Objectives:

- 1) To characterize the safety and tolerability of vorinostat in this patient population
- 2) To assess the time to response (TTR)
- 3) To assess the response duration (RD)
- 4) To evaluate progression free survival (PFS)
- 5) To assess overall survival (OS)

Secondary Objective 1 concerns toxicity and adverse events, hence will involve categorical variables. They will be tabulated via frequency distributions, and also dichotomized to report the proportion (and percentage) of patients experiencing a specified level (e.g., Grade 3-4) of toxicity. Analysis of these proportions (i.e., rates) will include both point and 90% confidence interval (CI) estimates, with the CI estimates calculated via Wilson's method. The 90% confidence level is appropriate for either the Stage 1 sample size (n=12) or even the Stage 2 sample size (n=29) planned for this Phase II trial.

Secondary Objective 2 concerns TTR, which is a continuous variable not subject to censoring. It will be summarized descriptively, reporting N, median, mean, standard deviation (SD), standard error (SE), minimum, maximum, and 90% CI for the mean calculated from the SE and asymptotic Normal distribution theory.

Secondary Objectives 3-5 concern censored time-to-event (TTE) endpoints. Their distribution will be estimated using standard survival analysis techniques, and the Kaplan-Meier (K-M) method. From the K-M life tables, both point and 90% CI estimates of various statistics of interest can be calculated (e.g., median, 6-month event-free rate, 12-month event-free rate, etc.). Statistical graphs of each K-M curve (with 90% CI lines) will be generated for visual display of these censored TTE endpoints.

There are 7 Exploratory Objectives:

- 1) To assess the association between a metabolic response by PET/CT after one cycle of chemotherapy and subsequent best tumor response according to standard anatomic response evaluation criteria (RECIST).
- 2) To assess the association between a metabolic response by PET/CT after the first and second chemotherapy cycle and PFS.
- 3) Flow sort diploid, aneuploid, and tetraploid populations of tumor cells from FFPE tissue blocks from patients who benefited from SAHA therapy and from patients who did not demonstrate a durable benefit.

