Exploratory Objective 2 concerns the potential association of PET/CT response (magnitude of decrease in SUV after 1 treatment cycle) with censored PFS. “PET response” (yes/no) will be determined as just described above for Exploratory Objective 1. At Stage 1 (n=12), to explore the potential association of PET/CT response with length of censored PFS, we will use the Cox proportional hazards model. This analysis will focus on the length of PFS after the second PET/CT scan, and will be exploratory only. The goal would be to determine if there is any hint of a potential positive association in the hypothesized *direction*, i.e., is the hazard ratio (HR) < 1 or not for patients with an early PET/CT response. At Stage 2 (n=29), we would repeat the same Cox model investigation, but pay more attention to the magnitude of (HR), its precision (i.e., half-width of its 90% CI), but not its statistical significance (i.e., p-value). Again, this Cox modeling investigation would still be viewed as exploratory only. A similar analysis will be performed utilizing the third PET/CT scan, taken after 2 treatment cycles, at day 56.

Exploratory Objectives 3, 4 and 5 are strictly exploratory and will be reported as descriptive results

Exploratory Objective 6 concerns yet another time-to-event endpoint (SDD), which is defined in [Section 10.1.5](#). The analysis of the censored SDD distribution will use the same approach as described above for [Secondary Objectives 3-5](#).

Exploratory Objective 7 concerns a biomarker (HR23B), measured by immunohistochemistry (IHC). Its expression level will be recorded as: 0, 1+, 2+, or 3+. In light of the small to modest sample sizes for this Phase II trial (either n=12 after Stage 1, or n=29 after Stage 2), we will dichotomize the total staining score (TSS) of HR23B into  $\geq 6$  (“positive”) or  $< 6$  (“negative”).

At Stage 1 (n=12), the association of HR23B’s dichotomized expression level (absence/presence) to objective response (yes/no) can be explored via a simple 2 x 2 contingency table. From the table we can compute the point and 90% CI estimates of response rates among the patients who do vs. those who do not “express” HR23B. The most basic exploratory observation will be the *direction* of the association, i.e., whether the point-estimate of response rate is higher (or lower) among expressers of HR23B. We can also observe the precision in the estimate of the response rate via its CI.

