**Confirmation:**

- To be assigned the status of PR or CR, changes in tumor measurements must be confirmed by repeat assessments that should be performed no less than 4 weeks after the criteria for response are first met. Longer intervals as determined by the study protocol may also be appropriate.
- To be assigned the status of SD, follow-up measurements must have met the SD criteria at least once after study entry at a minimum interval (in general, not less than 6-8 weeks) that is defined in the study protocol.

**Duration of Overall Response:** This is measured from the time measurement criteria are met for CR or PR (whichever status is recorded first) until the first date that recurrence or PD is objectively documented, taking as reference for PD the smallest measurements recorded since the treatment started.

**Duration of Stable Disease:** Stable disease is measured from the start of the treatment until the criteria for disease progression are met, taking as reference the smallest measurements recorded since the treatment started. The clinical relevance of the duration of SD varies for different tumor types and grades.

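### Response duration and stable disease duration end only at documented progression, so a Kaplan-Meier analysis would by implication censor deaths without it and overstate both durations relative to progression or death

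*Combined protocol and SAP*

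**What the plan says.** Section 10.1.5 runs RD from first meeting the criteria for CR or PR "until the first date that recurrent or progressive disease is objectively documented". For SDD it says: "Stable disease is measured from the start of the treatment until the criteria for progression are met". Appendix C, in the text on confirmation and durations, gives the same two rules, with RD again running "until the first date that recurrence or PD is objectively documented". Death is not an end event in any of these definitions.

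The next subsection, 10.1.6, defines PFS as the "duration of time from start of treatment to time of progression or death, whichever occurs first".

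Section 12.4 sets the analysis. "Secondary Objectives 3-5 concern censored time-to-event (TTE) endpoints", that is RD, PFS and OS. They are estimated by Kaplan-Meier with 90% confidence intervals, and the median and the 6- and 12-month event-free rates are given as examples of what will be reported. For SDD, "The analysis of the censored SDD distribution will use the same approach as described above". No rule says what happens to a patient who dies without documented progression, no censoring date is given, and no competing-risk method is named. Section 12.5.2 does count early death as failure, but only for the response rate.

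**The concern.** SDD and PFS both start at the start of treatment. For a patient with stable disease who dies before progression is documented, PFS records an event. SDD, under the stated definition and method, records none, and Kaplan-Meier treats that patient as still at risk of progressing later. RD has the same feature from the date of response.

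Such deaths are foreseeable. Section 5.3 lets patients leave for toxicity, intercurrent illness or withdrawal. Section 5.4 then follows them for 180 days or until death, and no scan schedule is set after the off-study assessment. Deaths can therefore be recorded where progression is not.

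What is at stake is the reading of the durations. Section 2.1 notes that most phase II trials in this disease report stable disease of 6 months or more and calls it a possibly relevant exploratory endpoint. An event-free rate against which death does not count would sit beside a PFS rate against which it does.

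**Working it through.** **The plan's own figures.** No design figure is stated for RD or SDD. The only stated figures are those of the two-stage response design in 12.1.1: stop at 0 of 12 responders, promising at 3 or more of 29, response rates 5% and 20%. Exact binomial calculation gives a probability of early termination of 0.95^12 = 0.540, alpha 0.148 (limit 0.15) and power 0.9005 (stated 0.90). They reproduce, and none depends on RD or SDD.

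**Inputs for the durations.** The end events come from 10.1.5, 10.1.6 and Appendix C, and the method from 12.4. The share w of RD or SDD endings that are deaths without documented progression is not in the documents. It is assumed here, mainly at 5%, 10% and 20%.

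**Formula.** Let the total hazard of progression or death be constant at h. Progression then has hazard (1-w)h.

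- Counting death as an event: S(t) = exp(-ht), median = ln2/h.
- Censoring death: S(t) = exp(-(1-w)ht), median = ln2/((1-w)h).
- Ratio of medians = 1/(1-w).

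The ratio does not depend on h. At w = 2% it is 1/0.98 = 1.02, and at w = 30% it is 1/0.70 = 1.43.

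**Illustration.** Assume also a progression-only median of 12 months. The death-censored curve is then 0.5^(6/12) = 70.7% at 6 months and 50.0% at 12 months, whatever w is. With death counted, the median is 12(1-w), and the rates are 0.5^(0.5/(1-w)) and 0.5^(1/(1-w)).

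| w | Inflation of median | Median, death counted (months; 12.0 if censored) | 6-month rate, death counted (70.7% if censored) | 12-month rate, death counted (50.0% if censored) |
|---|---|---|---|---|
| 5% | +5% | 11.4 | 69.4% | 48.2% |
| 10% | +11% | 10.8 | 68.0% | 46.3% |
| 20% | +25% | 9.6 | 64.8% | 42.0% |

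**Check by simulation.** This used Kaplan-Meier curves for 25 patients with an assumed progression-or-death median of 12 months. The typical median rises from 12.0 to 12.7 (w = 5%), 13.3 (10%), 15.1 (20%) and 17.2 months (30%), close to 12/(1-w) = 12.6, 13.3, 15.0 and 17.1.

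**Censoring date.** If deaths are censored at the date of death, the curve is never below the one that counts them. If they are censored at the last scan, it can dip slightly between that scan and the death and is higher afterwards. The plan does not say which applies.

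**The case against.** **The target may be different.** RD and SDD are defined as times to documented progression and PFS as something else. Two differently defined endpoints are not in themselves a contradiction. A reader might infer that the durations are biased estimates of what they claim to measure. The documents do not support that. The calculation above compares two estimands, and under its independent hazards censoring is unbiased for progression alone. Deaths without a scan in advanced cancer are probably related to progression, but nothing in the documents shows it. So the overstatement is relative to a progression-or-death duration.

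**Censoring of deaths is not written down.** This stands. It is an implication of leaving death out of the definitions and then using Kaplan-Meier without a competing-risk method.

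**The effect may be small.** This also stands. The Schema (Post-treatment Period) orders imaging at the end of study if none was done in the last 30 days. The study calendar requires radiologic documentation for removal due to progression. The note to the response table in 10.1.4.3 asks for every effort to document progression after treatment stops. Section 2.1 describes the disease as indolent. At w of 5% to 10% the 6-month rate moves by 1.3 to 2.7 points, less than one patient in 29 (3.4 points). A 90% interval around 50% with 29 patients is about ±15 points (1.645 × √(0.25/29) = 0.153). RD would rest on about 6 patients even at the target rate (0.20 × 29 = 5.8), and Section 8 mentions two partial responses.

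**PFS already gives a death-inclusive duration.** True, and it limits the harm. It does not cure an SDD or RD rate quoted on its own.

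**Changing one phrase would not be free.** Correct. Appendix C repeats the definitions, so editing 10.1.5 alone would create a new contradiction. Section 8 and Appendix D also show that some responses and stable-disease durations are already known.

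**Conclusion.** The point holds in a limited form. Followed as written, the plan leaves a death without documented progression as a censored observation for RD and SDD, and so reports higher event-free rates and longer medians than a duration ending at progression or death. The inflation of the median is 1/(1-w): +5%, +11% and +25% at w of 5%, 10% and 20%. This rests on constant hazards and on a w that the documents do not supply. The rates in the table rest in addition on an assumed 12-month progression-only median.

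A reader might also infer that the trial's conclusion on efficacy is at risk. It is not. RD is secondary and SDD exploratory, and the response decision rule, N = 29, alpha and power do not use them.

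**What to change.** - In 10.1.5 and in Appendix C, define RD and SDD as ending at documented progression or death from any cause, whichever comes first, in line with 10.1.6.
- In 12.4, state that patients alive without progression are censored at the last evaluable tumor assessment.
- Disclose the change and its date, and report the progression-only definition as a sensitivity analysis, because some outcomes are already known.

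Death dates are already needed for PFS and OS, so no new data, visits or patients are required. The cost is slightly shorter reported durations and one extra sensitivity analysis: a cheap improvement.

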#### **10.1.6 Progression-Free Survival**

Progression-Free Survival (PFS) is defined as the duration of time from start of treatment to time of progression or death, whichever occurs first.

### **10.2 Other Response Parameters**

#### **10.2.1 Time to Response (TTR)**

TTR is measured from the start of the treatment until the RECIST measurement criteria are met for CR or PR (whichever is first recorded). TTR only applies to the patients achieving either PR or CR, and involves no censoring.

#### **10.2.2 Overall Survival (OS)**

OS is measured from the start of treatment until death from any cause. OS is subject to censoring.

### **10.3 Response Review**

We do not routinely mark scans and will encourage all sites that submit radiographic images to submit unmarked images. After the initial patient recruitment, we will use an outside radiologist to review the scans prior to going to the second phase. If the decision is made to proceed to the second phase, an outside radiologist will look at all images at protocol completion.

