### **1.3 Exploratory Objectives**

- To assess the association between a metabolic response by PET/CT after one cycle of chemotherapy and subsequent best tumor response according to standard anatomic response evaluation criteria (RECIST).
- To assess the association between a metabolic response by PET/CT after the first and second chemotherapy cycle and PFS.
- Flow sort diploid, aneuploid, and tetraploid populations of tumor cells from FFPE tissue blocks from patients who benefited from SAHA therapy and from patients who did not demonstrate a durable benefit.
- Profile the genomes of each cell population using oligonucleotide CGH arrays. This will confirm the identification of tumor populations in each sample and provide genomic landmarks for NGS analysis.
- Perform whole exome analysis of the sorted tumor population and matching germ line sample for each of the patients selected
- To assess stable disease duration (SDD)
- To assess the association between response to vorinostat treatment and HR23B on tumor paraffin blocks
- Retrospectively compare volumetric density (viable tumor volume=VTV) with pre-determined RECIST of target lesions in cross sectioning imaging (CT/MR) already obtained
- Correlate VTV, RECIST and treatment response (partial response, stable disease, progressive disease and stable disease over 6 months)

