| Head and Neck   | Brun(64)      | 2002        | 47**     | median*         | >120                   | 40                   | 0.004          |
| Ovarian   | Avril (65)    | 2005        | 33       | -20%            | 38                     | 23                   | 0.008          |
| Lung  | Weber(65)     | 2003        | 57       | -20%            | 9                      | 5                    | 0.005          |
|   | Hoekstra (66) | 2005        | 56       | -35%            | 43                     | 18                   | 0.04           |

\* Median metabolic rate at the time of the follow-up study.

\*\* Chemoradiotherapy, otherwise chemotherapy.

Thus, FDG-PET has the potential to improve patient management by signaling the need for early therapeutic changes in non-responders, thereby avoiding the side effects and costs of ineffective treatment. Furthermore, as an early indicator of clinical benefit, FDG-PET may also facilitate oncologic drug development by shortening Phase II trials and detecting clinical benefit earlier in Phase III investigations.

An exploratory objective of this study (pending funding) will be to assess the association between a metabolic response after one and two cycles of chemotherapy and subsequent best tumor response according to standard anatomic response evaluation criteria (RECIST 1.1). The PET studies will be optional.

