Use of MRI remains a complex issue. MRI has excellent contrast, spatial, and temporal resolution; however, there are many image acquisition variables involved in MRI, which greatly impact image quality, lesion conspicuity, and measurement. Furthermore, the availability of MRI is variable globally. As with CT, if an MRI is performed, the technical specifications of the scanning sequences used should be optimized for the evaluation of the type and site of disease. Furthermore, as with CT, the modality used at follow-up should be the same as was used at baseline and the lesions should be measured/assessed on the same pulse sequence. It is beyond the scope of the RECIST guidelines to prescribe specific MRI pulse sequence parameters for all scanners, body parts, and diseases. Ideally, the same type of scanner should be used and the image acquisition protocol should be followed as closely as possible to prior scans. Body scans should be performed with breath-hold scanning techniques, if possible.

PET-CT At present, the low dose or attenuation correction CT portion of a combined PET-CT is not always of optimal diagnostic CT quality for use with RECIST measurements. However, if the site can document that the CT performed as part of a PET-CT is of identical diagnostic quality to a diagnostic CT (with IV and oral contrast), then the CT portion of the PET-CT can be used for RECIST measurements and can be used interchangeably with conventional CT in accurately measuring cancer lesions over time. Note, however, that the

PET portion of the CT introduces additional data which may bias an investigator if it is not routinely or serially performed.

Ultrasound Ultrasound is not useful in assessment of lesion size and should not be used as a method of measurement. Ultrasound examinations cannot be reproduced in their entirety for independent review at a later date and, because they are operator dependent, it cannot be guaranteed that the same technique and measurements will be taken from one assessment to the next. If new lesions are identified by ultrasound in the course of the study, confirmation by CT or MRI is advised. If there is concern about radiation exposure at CT, MRI may be used instead of CT in selected instances.

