- 4) Profile the genomes of each cell population using oligonucleotide CGH arrays. This will confirm the identification of tumor populations in each sample and provide genomic landmarks

for NGS analysis.

5) Perform whole exome analysis of the sorted tumor population and matching germ line sample for each of the patients. The combined aCGH and exome data will be mined to identify genes and pathways that are targeted by select somatic events in each of the patient subsets

6) To assess stable disease duration (SDD).

7) To assess the association between response to vorinostat treatment and HR23B on tumor paraffin blocks.

Exploratory Objective 1 concerns the potential association of PET/CT response (magnitude of decrease in SUV after 1 treatment cycle) with clinical response by RECIST 1.1 criteria. Percent change in SUV ( $\Delta$ SUV) is a continuous variable, whereas objective response is a categorical (typically, binary) variable. First, we will use receiver operator characteristic (ROC) curve analysis to determine the optimal cutoff in the distribution of  $\Delta$ SUV, in relationship to objective response (yes/no). That will allow us to define “PET response”. We will also compare the descriptive statistics of the  $\Delta$ SUV distribution in the RECIST responders vs non-responders. At Stage 1 (n=12), the association of  $\Delta$ SUV with subsequent best tumor response will be explored in a simple 2 x 2 contingency table, with point and 90% CI estimates of objective response rates among the patients with vs. without PET response. Descriptively only, we can then examine the point and CI estimates to see if there is a hint of any association. At Stage 2 (n=29), we would repeat the same descriptive, exploratory investigation, and then determine what, if any, additional statistical analysis might be appropriate. For example, that might involve exact logistic regression to model the log-odds of later objective response as a function of only one predictor: early PET response (yes/no). This exact logistic modeling investigation would still be viewed as exploratory only, but would yield a point and 90% CI estimate of the odds ratio for response.

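### The RECIST outcome used in the exploratory PET analyses (Objectives 1 and 2) is not protected from PET information

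*Combined protocol and SAP*

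**What the plan says.** Section 1.3 gives the first PET aim: "To assess the association between a metabolic response by PET/CT after one cycle of chemotherapy and subsequent best tumor response". The second aim relates PET response to PFS.

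Section 12.4 says Objective 1 concerns "the potential association of PET/CT response (magnitude of decrease in SUV after 1 treatment cycle) with clinical response by RECIST 1.1 criteria". It uses ROC "analysis to determine the optimal cutoff in the distribution of" percent SUV change, with RECIST response (yes/no) as the reference. The resulting PET response then enters a Cox model for Objective 2: "This analysis will focus on the length of PFS after the second PET/CT scan, and will be exploratory only". A similar analysis follows for the day 56 scan.

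On how RECIST is read:

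- Section 10.1.3 (PET-CT) lets the CT part of a PET-CT be used for RECIST if its diagnostic quality is documented. It adds that the "PET portion of the CT introduces additional data which may bias an investigator if it is not routinely or serially performed".
- Section 10.1.3 (FDG-PET) lets a positive follow-up PET after a negative baseline PET count as progression by a new lesion, and lets PET upgrade a response to CR.
- Appendix C includes set-ups in which the RECIST CT and the PET are both done on the fusion scanner.
- Section 10.3 plans an outside review before the second phase, and says that at the end "an outside radiologist will look at all images at protocol completion". The study "will encourage all sites that submit radiographic images to submit unmarked images".

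The only stated reader blinding is in Section 8: the research assistant doing volumetric segmentation is blinded to clinical status. PET is optional and depends on funding (Schema; Section 9, note L).

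**The concern.** An analysis of whether early PET change predicts RECIST outcome needs an outcome assessed without knowledge of PET. If the reader knows the PET result, or if PET is allowed to settle the RECIST call, part of any association is built in by the assessment.

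The plan names the hazard in Section 10.1.3 but no masking rule follows. It also permits PET inside the outcome and does not say whether the site or the outside read feeds the PET analyses. Because the cutoff is tuned to the same response, an influenced call would also enter the definition of PET response. At stake is whether a positive (or null) PET finding could be told apart from reader influence.

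**Working it through.** **1. The plan's own figures.** Inputs from Section 12.1.1: 12 patients, continue if at least 1 responds; 29 in total, promising if at least 3 respond; rates 5% and 20%.

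- Early termination at 5%: 0.95^12 = 0.5404 (stated 0.540).
- P(promising) = sum over x = 1 to 12 of P(Bin(12,p) = x) × P(Bin(17,p) ≥ max(0, 3 − x)). This gives 0.1480 at 5% (stated level 0.15) and 0.9005 at 20% (stated power 0.90).
- Expected size at 5%: 12 + (1 − 0.5404) × 17 = 19.8.

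The design reproduces. No PET quantity enters it, so masking changes none of these figures.

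**2. Where PET can reach the outcome.**

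| Route | Section | Effect on Objectives 1 and 2 |
|---|---|---|
| PET-based new lesion counts as progression | 10.1.3, FDG-PET | Can change the PFS time and best response |
| PET upgrade to CR | 10.1.3, FDG-PET | PR to CR leaves the patient a responder |
| RECIST CT taken from the PET/CT session | 10.1.3, PET-CT; Appendix C | No rule separates the PET data from the CT read |
| PET and first scheduled RECIST scan in the same window, day 56 ± 3 | Schema | Both can be available at one time point |
| Outside review | 10.3 | PET neither included nor excluded |

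The first two routes rest on visual PET findings, not on SUV change, so their link to the predictor is indirect.

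**3. How much one or two calls can move the table.** The number of patients with PET is not given. Assume all 29 have it; with fewer, each call generally weighs more.

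- One call, assumed 14/15 split. At 1/14 against 1/15, the odds ratio is (1/13)/(1/14) = 1.08. At 2/14 against 1/15 it is (2/12)/(1/14) = 2.33. Read in reverse, one call removes the apparent association. The two-sided Fisher p-value for the second table is 0.60. The 90% Wilson intervals are 4.8% to 35.3% and 1.5% to 25.1%.
- Two opposite calls, assumed 10/19 split. At 1/10 against 2/19, the odds ratio is (1/9)/(2/17) = 0.94. At 2/10 against 1/19 it is (2/8)/(1/18) = 4.5. Total responders stay at 3 of 29. P(2 or more of the 3 responders fall in the group of 10) = (45 × 19 + 120)/3654 = 0.27, which is also the two-sided Fisher p-value.

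Small responder numbers are realistic: Section 8 and Appendix D mention two partial responses in this trial. They do not say whether those patients had PET.

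**4. A diffuse version.** Assume no true association, equal PET groups, response rate p, and a share b of borderline patients, half of whom a masked reader would call responders. An unmasked reader shifts the call probability by d toward the PET result. The rates become p + bd and p − bd, and the induced odds ratio is [(p + bd)/(1 − p − bd)] / [(p − bd)/(1 − p + bd)].

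| p | b | d = 0.25 | d = 0.50 |
|---|---|---|---|
| 20% | 5% | 1.17 | 1.37 |
| 20% | 10% | 1.37 | 1.89 |
| 20% | 20% | 1.89 | 3.86 |
| 5% | 5% | 1.71 | 3.16 |

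Example: p = 20%, b = 10%, d = 0.25 gives (0.225/0.775)/(0.175/0.825) = 1.37. The documents give neither b nor d; these are ranges, not estimates.

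**The case against.** The other side has good points.

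- **Outside review.** Section 10.3 speaks of scans and radiographic images and contrasts an early review with a final one. On that reading, all images most naturally means the scans of all patients. A reader might infer that the outside radiologist is shown PET or SUV change; the text does not say so. Under Appendix B, SUV is computed from region averages, injected dose and body weight, and is not simply seen. Outside review, with unmarked images encouraged, is itself a partial safeguard.
- **Site readers.** A reader might also infer that they hold the PET results when reading later CTs. No section says who receives them. The remark in Section 2.3 that "FDG-PET has the potential to improve patient management by signaling the need for early therapeutic changes in non-responders" is general background, not a release rule.
- **The caution in 10.1.3.** It concerns PET that is not routine or not serial. Optional PET may not be routine, but patients who have it are scheduled at baseline, day 28 and day 56.
- **Response is hard to manufacture.** PR needs a 30% decrease in summed diameters, with confirmation.
- **Little rests on it.** The analyses are optional and exploratory, and Section 12.4 looks only descriptively for a hint of association. The illustrated tables are far from conventional significance.

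These points limit the size of the concern and rule out treating reader exposure as fact. They leave the gap itself: PET-based progression calls are expressly allowed, no rule keeps PET from the RECIST reader, and the read used for the PET analyses is not named.

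**Conclusion.** The point holds in a limited form. The RECIST outcome in Objectives 1 and 2 is not protected from PET, and the plan both permits PET inside that outcome and tunes the SUV cutoff to it. With few responders, one or two influenced calls could create or remove the apparent association: 1.08 to 2.33 with one call, 0.94 to 4.5 with two. These rest on assumed PET splits and on every patient having PET. They show fragility, not that any call was changed.

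It is tempting to conclude that the primary response count is biased as well. The documents do not show this. The two-call example leaves 3 of 29 responders before and after. The one-call example moves the total from 2 to 3, the threshold for promising, but only because an extra responder was assumed. The Simon figures stand as stated. The consequence is confined to optional exploratory analyses, so this is a worthwhile refinement and not a threat to the trial's main conclusion.

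**What to change.** In Sections 10.3 and 12.4, state that for Exploratory Objectives 1 and 2:

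- the response and progression outcome is the RECIST 1.1 read of the outside radiologist already planned in 10.3;
- that read uses diagnostic CT/MRI only, without PET images, SUV values or PET reports;
- PET-based new-lesion progression and PET upgrades to CR do not count toward this outcome.

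Where the RECIST CT came from a PET/CT session, the CT series alone is supplied.

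The cost is wording and the way images are packaged for a review already planned. No extra reader or scan is needed, and the read can be made from stored images. The masked outcome may differ from the site-read response in a few patients, so the differences should be reported. Any patient taken off study on a PET-based progression call may lack later CT/MRI; such patients should be listed and their censoring rule stated. The change concerns only the outcome used in these two analyses and leaves the conduct of treatment as it is.
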